- ^t PET scanning (if subject has consented to optional substudy) will be performed with a locally approved amyloid β imaging agent, eg, Amyvid, if available or an agent under clinical investigation if

no agents are approved locally; the imaging agent must remain unchanged for an individual subject throughout the study. A PET scan will only be performed at an ED Visit if the subject has been treated with study drug for at least 39 weeks.

- ^u Site staff will contact the subject or the study partner the day before the PK blood sampling to provide instructions that subjects must not take their study drug at home on the day of the PK blood sampling. During this telephone contact with the subject or the study partner, the site staff should document the time that the subject took their study drug that day, ie, the day before the PK blood sampling.
- ^v Two plasma PK samples will be obtained: 1 sample at predose (trough) and another sample 1 to 6 hours postdose at Visits 3, 4, 6, 7, 9, and 11 and another sample 4 to 8 hours postdose at Visit 13 (or ED). Therefore, subjects or their study partners must be instructed not to take their study drug at home on the day the PK sampling is performed. Instead, subjects will take the study drug at the clinic after collection of the predose PK sample. At Visit 13 (or ED) the PK blood sample should be collected shortly before or after completing the LP for subjects participating in the CSF substudy. If at an ED Visit, the subject has already stopped study drug, then no dosing will take place, but the trough PK sample will still be collected. For subjects participating in the CSF substudy who have stopped taking study drug prior to the ED visit, the LP should be performed at approximately the same time as at the Screening Visit, and then a trough PK sample will be collected either shortly before or shortly after the LP.
- ^w PD and exploratory biomarker blood samples should be collected at fasting or at least 2 hours after the most recent meal and, as far as is feasible, samples should be taken at the same time of day at all visits. Samples should be taken predose at Visits 3, 4, 6, 7, 9, 11, 13 (or ED), 14, and 15. (revised per Amendments 01 and 03)
- ^x For subjects who consent to participate in the CSF longitudinal substudy. Visit 13 (or ED) also includes blood PK and PD assessments and so the subject will be dosed at the clinic on these days. A CSF sample will be collected by LP between 4 and 8 hours postdose and at the same time of day as the subject's Screening LP (± 1 hour). The CSF sample will be taken with the subject fasting (preferred) or at least 2 hours after the most recent meal. A gravity drip collection method must be used. If performed on the same day as the cognitive tests, the LP will be performed after the cognitive tests; the subject should rest and drink some fluid to hydrate after the cognitive tests and before the LP. Subjects will be encouraged to stay at the site after completion of LP for medical observation. The CSF sample will not be taken at the ED Visit if this visit occurs within 3 months of a previous CSF sample. If at an ED Visit, the subject has already stopped study drug, then no dosing will take place, but the CSF sample will still be collected unless it was already collected within the past 3 months. Subjects receiving concomitant anticoagulation/antiplatelet therapy should have prothrombin time and INR (derived from prothrombin time) prior to LP; if they are assessed by the investigator to be at risk for bleeding, they are to be excluded from CSF collection. Note that subjects who are assessed by both amyloid PET and CSF A β (1-42) are required to wait for a minimum of 48 hours between the 2 procedures. (revised per Amendments 01 and 02)
- ^y Subjects reporting AEs relating to abnormal dreams, nightmares, or sleep terror will be questioned on the nature, frequency, and impact of these events.
- ^z AEs that might indicate signals of possible drug abuse potential require a more detailed follow-up through completion of a specific eCRF form (Possible drug abuse potential form/ questionnaire); categories and examples of AEs indicating signals of possible drug abuse are provided in [Appendix 3](#). (revised per Amendments 02)
- ^{aa} The 1st dose of study drug will be given to the subject at the study site and the subject will be encouraged to stay at the site for an appropriate period of time for postdose medical observation.

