A blood sample will be obtained at Screening and will be used to determine the *ApoE* genotype of subjects enrolled in this study. The findings will be used in the statistical analysis to determine the effects on treatment response and safety. (revised per Amendment 01)

The genomic DNA samples will be stored and may also be used to examine the role of genetic variability in subjects' absorption, distribution, metabolism, and excretion, the development of AEs, or underlying AD. Variations in elenbecestat (E2609) exposure or the occurrence of AEs observed in the study population may be evaluated by correlation of single-nucleotide polymorphisms with PK, safety, or PD data.

Details of PGx testing may be provided and reported separately.

Amyloid PET

An amyloid PET scan may be performed at Screening to confirm deposition of amyloid in the brain. A historical amyloid positive PET scan may be used if conducted within 12 months before the planned date of randomization and provided that the scan and result are considered acceptable by the central PET reading group. As part of an optional substudy, longitudinal amyloid PET imaging will also be conducted after 12 and 24 months of treatment (or at ED, provided the subject has received at least 39 weeks of study drug). Longitudinal amyloid PET imaging will only be conducted on subjects that have consented to this optional substudy and who have had Screening PET scans performed for this study (ie, historical scans cannot be used for the longitudinal analyses).

Descriptions and detailed instructions for all amyloid PET imaging can be found in the PET imaging manual provided to the study PET imaging facilities.

Further details regarding pharmacodynamics, pharmacogenomics, and other biomarker research is provided in [Appendix 4](#).

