9.5.2 Schedule of Procedures/Assessments

9.5.2.1 Schedule of Procedures/Assessments

Table 2 presents the schedule of procedures/assessments for the Prerandomization Phase (see below).

Table 3 presents the schedule of procedures/assessments for the Randomization Phase.

Table 2 Schedule of Procedures/Assessments in Study E2609-G000-301: Prerandomization Phase

Phase	Prerandomization
Period	Screening
Visit	1
Procedures/ Assessments (to be completed in a maximum of 50 days, plus an additional window of up to 30 days if required)	
Inclusion and exclusion criteria	X (All tiers)
Prior / concomitant meds including AD meds	X (All tiers)
Adverse events	X (All tiers)
Informed consent (subject and study partner)	X (Tier 1)
Optional subject informed consent to CSF and PET substudies ^a	X (Tier 1)
Demographics	X (Tier 1)
Medical history (including cognitive impairment history)	X (Tier 1)
Clinical diagnosis and disease staging ^b	X (Tier 1)
MMSE ^c	X (Tier 1)
ISLT total recall, CBB, and ISLT delayed recall ^c	X (Tier 1)
CDR ^c	X (Tier 1)
Modified Hachinski ischemic scale	X (Tier 1)
EQ-5D ^d	X (Tier 2)
QOL-AD ^c	X (Tier 2)
Zarit's Burden Interview of study partner	X (Tier 2)
C-SSRS	X (Tier 2)
Complete physical exam including dermatologic review	X (Tier 3)
Full neurologic examination	X (Tier 3)
Vital signs ^f	X (Tier 3)
Height, weight, and BMI	X (Tier 3)
Single 12-lead ECG ^g	X (Tier 3)
Blood samples for clinical chemistry, hematology, coagulation, thyroid function, vitamin B12 ^h (revised per Amendmemnt 02)	X (Tier 3)
Blood samples for PG ⁱ	X (Tier 3)
Blood samples for PD and other biomarkers ^j	X (Tier 3)
Blood sample for immunologic assessments,	X (Tier 3)

Table 2 Schedule of Procedures/Assessments in Study E2609-G000-301: Prerandomization Phase

including isolation of PBMCs for storage and testing as required (revised per Amendment 03)	
Blood for viral screen ^k	X (Tier 3)
Serum pregnancy test ^l	X (Tier 3)
Urinalysis (central lab)	X (Tier 3)
MRI including vMRI and fMRI (for PD) ^m	X (Tier 4)
Amyloid PET (for eligibility and longitudinal PET baseline) ⁿ	X (Tier 5)
CSF sampling (for eligibility and PD/exploratory biomarker baseline) ^{n,o,p} (revised per Amendment 03)	X (Tier 5)

NOTES:

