- Screening assessments/procedures have been organized into 5 distinct tiers. All assessments and procedures in each tier should be completed, and eligibility to continue confirmed, before any assessments/procedures from the next tier commence. Tier 2 and Tier 3 procedures may be performed on the same day as Tier 1 procedures, as long as the results of the procedures from the earlier Tier(s) show that the subject is eligible to continue with screening activities.
- All screening assessments are to be completed within 50 days, plus an additional window of up to 30 days if required. Visit 2 (Randomization) should occur as soon as possible after completion of all Screening assessments/procedures and confirmation of eligibility to continue in the study, and no more than 10 days after completion of the last screening assessment (amyloid eligibility assessment).

AD = Alzheimer’s disease, ApoE = apolipoprotein E, BMI = body mass index, CBB = Cogstate Brief Battery, CDR = Clinical Dementia Rating, CSF = cerebrospinal fluid, C-SSRS = Columbia Suicide Severity Rating Scale, ECG = electrocardiogram, EQ-5D = EuroQol-5 Dimensions, fMRI = functional MRI (to be performed task free at resting state), INR = International Normalized Ratio, ISLT = International Shopping List Task, MMSE = Mini Mental State Examination, MRI = magnetic resonance imaging, PBMCs = peripheral blood mononuclear cells, PD = pharmacodynamic, PET = positron emission tomography, PG = pharmacogenomic, PK = pharmacokinetic, QTc = corrected QT interval, QOL-AD = Quality of Life in Alzheimer’s Disease, vMRI = volumetric MRI.

- a: Subjects should be informed about the optional CSF and PET longitudinal substudies as part of Tier 1 of the Screening Visit. However, subjects are able to consent to 1 or both substudies at any time up to Tier 5 of the Screening Visit. Furthermore, subjects who have an amyloid PET for eligibility (Tier 5) may consent to the PET substudy after Tier 5, ie during the Randomization Phase of the study. Similarly, subjects who provide a CSF sample for eligibility (Tier 5) may consent to the CSF substudy after Tier 5, ie during the Randomization Phase of the study.

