- j: The blood samples taken for PD and exploratory biomarkers should be collected at fasting or at least 2 hours after the most recent meal. For subjects who are going to provide a CSF sample at Tier 5 for amyloid eligibility and/or PD/exploratory biomarker baseline purposes, the timing of the blood draw for PD and exploratory biomarkers should be at approximately the same time of day as planned for the LP. (revised per Amendment 03)

-
- k: Viral screen to include HCVAb (Hepatitis C) and HBsAg (Hepatitis B).
 - l: Only required for female subjects of child-bearing potential
 - m: For subjects who are approved for rescreening, MRI and vMRI need not be repeated if the date of the rescreen is no more than 90 days from the date of the original screening MRI.
 - n: PET scanning will be performed with a locally approved amyloid imaging agent (eg, Amyvid, if available or an agent under clinical investigation if no agents are approved locally); for subjects participating in the PET substudy, the imaging agent must remain unchanged throughout the study. Subjects who are assessed by both amyloid PET and CSF are required to wait for a minimum of 48 hours between the 2 procedures (revised per Amendment 02). A positive amyloid result is needed for only 1 of the 2 amyloid eligibility procedures to confirm eligibility (ie, even if 1 of the 2 results is negative for amyloid, the subject would still be eligible under the other, positive result). For subjects who are approved for rescreening, the amyloid PET need not be repeated for eligibility if confirmed amyloid positive during the original screening procedure. If a rescreened subject will participate in the longitudinal PET substudy, quantitative PET collection should be repeated if the original PET collection was done greater than 6 months from the date of the original screening procedure.

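### Table 2 footnote n dates the repeat-PET rule for rescreened subjects from the original screening, so it does no work for any scan that can serve as the longitudinal PET baseline

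*Protocol*

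**What the plan says.** Section 9.5.2.1, Table 2, places the amyloid PET in Tier 5 of screening, where it is both an eligibility test and the baseline for the longitudinal PET substudy. The notes to the table bound that screening: "All screening assessments are to be completed within 50 days, plus an additional window of up to 30 days if required".

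Footnote n then deals with subjects approved for rescreening. For eligibility, "the amyloid PET need not be repeated for eligibility if confirmed amyloid positive during the original screening procedure", with no time limit. For the substudy, the quantitative scan is to be repeated "if the original PET collection was done greater than 6 months from the date of the original screening procedure". The Amendment 02 version of the protocol has the same sentence.

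Footnote m, just before it, covers MRI. A repeat is waived "if the date of the rescreen is no more than 90 days from the date of the original screening MRI".

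Section 9.5.1.4.2 limits the longitudinal PET analyses to subjects whose screening PET was performed for this study: "historical scans cannot be used for the longitudinal analyses". Historical scans are accepted for eligibility only, within 12 months of planned randomization. The endpoint that depends on the baseline scan is the change in the amyloid PET SUVR composite at 24 months (Section 9.7.1.1.4).

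**The concern.** The sentence in footnote n appears intended to stop an outdated scan from serving as the quantitative baseline. To do that it must measure the age of the scan at the time the subject comes back. It measures instead the distance between the scan and the screening in which the scan was taken, and that distance is short by construction.

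If the rule is followed as written, a rescreened substudy subject keeps the original study scan as baseline however long ago the first screening was, unless something outside the available text intervenes. The 24-month change in SUVR then begins before treatment does, by an amount that differs between subjects. Sites may also diverge, some applying the literal wording and some its apparent purpose.

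**Working it through.** The plan gives no figure to reproduce; the check is date arithmetic.

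**Inputs**
- Screening window: 50 days plus up to 30 more (notes to Table 2).
- Position of the PET: Tier 5, inside that window (Table 2).
- Threshold: 6 months, taken as 180 to 184 days (footnote n).
- Rescreen dates: assumed, because the available text gives no rescreening interval.

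**Step 1: can a study PET meet the condition?**
Largest gap from the start of original screening to the PET = 50 + 30 = 80 days. Shortfall against 6 months = 180 − 80 = 100 days, up to 184 − 80 = 104 days. The condition cannot be met.

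**Step 2: can any other scan meet it?**
A historical scan can: "A historical amyloid positive PET scan may be used if conducted within 12 months before the planned date of randomization". Such a scan may lie more than 6 months before the original screening. However, Section 9.5.1.4.2 already excludes it as a longitudinal baseline, so the rule adds nothing there.

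**Step 3: literal anchor against rescreen anchor.**
Let p be the day of the PET (0 to 80, so 81 possible days) and R the day of the rescreen, both counted from the start of original screening, with 6 months taken as 182.5 days. The literal rule repeats the scan if p > 182.5. The rescreen-anchored rule repeats it if R − p > 182.5. Scan age at rescreen runs from R − 80 to R.

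| Assumed rescreen day R | Scan age at rescreen (days) | Literal rule: repeats | Rescreen-anchored rule: repeats |
|---|---|---|---|
| 120 | 40 to 120 | 0 of 81 | 0 of 81 |
| 200 | 120 to 200 | 0 of 81 | 18 of 81 |
| 270 | 190 to 270 | 0 of 81 | 81 of 81 |
| 365 | 285 to 365 | 0 of 81 | 81 of 81 |
| 730 | 650 to 730 | 0 of 81 | 81 of 81 |

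For R = 200 the anchored rule needs p < 17.5, that is days 0 to 17, which gives 18 days. These counts are possible PET days, not expected proportions of subjects.

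**Step 4: does another provision cap the scan's age?**
- The eligibility waiver in footnote n has no time limit.
- The 12-month limit applies to historical scans used for eligibility.
- The notes to Table 2 allow at most 10 days from the last screening assessment, named as the amyloid assessment, to randomization. They do not say how this applies when the PET is waived at rescreen, so it is not a clear cap.

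**Step 5: effect on the interval (illustration).**
The scan's age at first dose is an assumption. At 6 months the change spans 24 + 6 = 30 months; at 12 months it spans 24 + 12 = 36 months.

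**The case against.** Several points on the other side have force.

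- **The rule is not strictly impossible to trigger.** A historical scan could meet the condition. This stands, and it means one cannot say the rule never triggers. It does not rescue the rule, because such a scan is already excluded as the longitudinal baseline.
- **The available text is partial.** Rescreening requires an approval whose terms are not visible, and PET procedures are detailed in an imaging manual. This also stands. A reader might infer that the protocol accepts a baseline scan of any age; what can be said is only that no limit appears in the text available.
- **There is no conflict with the exclusion of historical scans.** A reader might infer one. Section 9.5.1.4.2 excludes scans by origin, not by age, and a PET from the subject's own earlier screening for this study is not shown to be historical.
- **The extra interval precedes randomization.** A reader might infer bias in the treatment comparison. Pre-treatment amyloid change should be balanced between randomized arms, and the endpoint is compared between arms (Section 9.7.1.7.3), so the expected harm is noise and a mislabelled interval.
- **The intended anchor is inferred.** The protocol does not state it. Footnote m supports the inference, and the rescreen date is the reading that gives the sentence a function.

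**Conclusion.** The point holds as a mis-stated reference date in an operative rule. For every scan that can serve as the longitudinal baseline, footnote n as written requires no repeat: the gap it measures is at most 80 days against a threshold of 180 to 184. This rests on the PET having been done within the stated screening window.

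The consequence is limited. Some rescreened subjects may contribute an SUVR change with an untreated lead-in of unspecified length, which adds variability and makes the 24-month label inaccurate for them. The lead-in of 6 to 12 months is illustrative, and no effect on the SUVR contrast has been quantified. The number of rescreened substudy subjects is not given and is probably small. The substudy is optional, its endpoint is a biomarker tested without multiplicity adjustment, and the primary CDR-SB analysis is not touched. It is a minor point, worth correcting because the correction is simple.

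**What to change.** Reword footnote n so that quantitative PET is repeated when the original PET collection was more than 6 months before the date of the rescreen. This keeps the protocol's own threshold and uses the same anchor as footnote m.

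The new anchor does not cover everyone. Footnote a lets subjects with an eligibility PET consent to the substudy during the Randomization Phase, and a subject who consents after dosing can no longer have a new pre-treatment scan. The age check should therefore be made at rescreen, or the baseline scan age of those subjects should be flagged in the analysis.

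The cost is one phrase in footnote n, a scan-age flag for late consenters, and a repeat scan for the subjects the rule was evidently written to catch.
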